### 16.1 Study endpoints:

Primary endpoint for phase I:

MTD of combination of Daratumumab and donor lymphocyte infusion

Primary endpoint for phase II:

Overall response rate to Daratumumab and DLI in patients with post-HCT relapsed AML and MDS

Secondary endpoints for phase II:

- ORR in MRD positive patients and in patients with overt morphological relapse
- MRD conversion rates
- 6 month post-relapse progression-free survival
- 6 month post-relapse overall survival
- 3 month GVHD rate

### 16.2 Analysis methods:

Analysis datasets:

Efficacy sets: All evaluable patients will be included in the analysis of the primary endpoint. The term evaluable is defined as any eligible patient who receives at least one dose of Daratumumab, does not withdraw consent, and is evaluated for response week 8; patients who fail to have a week-8 assessment due to early progression, death or toxicity will also be considered evaluable for response and categorized as non-responders. Patients who fail to have a week-8 assessment for other reasons (e.g., refusal due to travel constraints) will be considered unevaluable and will not be included in the denominator when calculating ORR rate.

Safety sets: The safety analysis dataset will include all eligible patients who receive one dose of daratumumab.

The adverse events will be examined and worst grade adverse events will be recorded for each patient and summarized by type, severity, and attribution (if possible) using NCI CTCAE version 4 criteria. Tolerability of the regimen will be assessed by summarizing the number of patients who require dose modifications and/or dose delays. In addition, we will also capture the proportion of patients who go off treatment due to adverse events or even those who refuse further treatment for lesser toxicities that inhibit their willingness to continue participation on the trial. All patients who have received at least one dose of daratumumab will be evaluable for toxicity and tolerability.

The primary endpoint of phase II is to evaluate overall response rates (ORR) to the combination of Daratumumab and DLI. The ORR will be defined as complete remission (CR), complete remission with incomplete marrow recovery (CRi), partial remission (PR) and morphological leukemia free

Date of protocol: 10/14/2020

IRB Approval Date: 11/24/2020

Version of protocol: 7

IND number: 139015

Institutional protocol number: OSU 17102

state (MLFS). The proportion of patients achieving ORR among efficacy sets will be calculated and 95% confidence interval will be estimated. In addition, the ORR among patients who received at least 3 doses of Daratumumab and DLI will be calculated as well. The ORR rate among MRD positive patients and patients with overt morphological relapse will be estimated as well. The MRD conversion rate from MRD positive to MRD negative, and the 3-month GVHD rate (both grade II-IV and III-IV) will be similarly analyzed.

Demographical and clinical characteristics of study patients will be described using mean and standard deviation, median and range, or frequency and percent depending on the data type and distribution. Overall survival (OS) will be defined as the time from the first treatment of Daratumumab to death or last contact date if no death. Progression free survival (PFS) will be defined as the time from the first treatment of Daratumumab to the date of progression or death or last clinical assessment date if no progression or death. Kaplan-Meier curves will be generated to estimate OS/PFS at 6 months. The association between patient characteristics and OS/PFS will be evaluated in univariable Cox proportional hazard regression model.

To examine the rate of GVHD (both grade II-IV and III-IV), the event will be onset of GVHD and time to GVHD will be defined as the period of time from first treatment of Daratumumab to the onset of GVHD. Death and early relapse without GVHD will be competing risks. Cumulative incidence rate of GVHD at 3-month with 95% confidence intervals will be estimated from the cumulative incidence curves. Competing risk regression analysis will be conducted to estimate the association between patient characteristics and GVHD.

For pre/post-treatment comparisons in the correlative part of the study, a paired t-test will be applied. Two-tailed p values <0.05 will be considered statistically significant in all analyses.

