## 12.3 COMPLETION OF TREATMENT

Treatment with study drug may be discontinued for any of the following reasons:

Adverse event.

Protocol violation.

Unsatisfactory therapeutic response.

Study terminated by sponsor.

Withdrawal by subject.

Lost to follow-up.

Other

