If a patient in dose level 1 receives less than 3 doses of Daratumumab due to reasons other than toxicity, then this patient will not be evaluable for DLT and will be replaced. An additional patient will be added to the dose cohort. For dose level 2 or 3, if a patient does not receive 3 doses of Daratumumab and DLI due to reasons other than toxicity, then this patient will not be evaluable and will be replaced. There will be no intrapatient dose escalation. Phase I may involve as few as 3 patients (three at the starting dose level if  $\geq 2$  DLTs are experienced) and a maximum of 18 patients will be treated, six at each of the 3 dose levels. We assume that 10% of the patients in this group will not be evaluable due to not finishing the DLT observation period. So we expect to accrue a minimum of 4 patients and a maximum of 20 patients.

At OSU, 125 patients with AML/MDS underwent allo-HSCT in 2012 and 2013. Among these, 32 patients relapsed. About 40% were from related donor and 60% from unrelated donor. So we expect to accrue approximately 6 patients for the related sibling donor cohort and 10 patients for the unrelated donor cohort per year. Hence, the minimum study duration for phase I would be about 8-10 months and the maximum study duration would be around 2.5-3.5 years (accounting for the DLT observation period) for related sibling donors and unrelated donors respectively.

After the MTD has been established, we will expand to Phase II trial. For phase II part, considering that patients receiving transplant from related sibling donor or unrelated donor with each treated at the corresponding MTD of Daratumumab plus DLI are expected to have similar profiles for response and toxicities, we will combine these 2 cohorts together in phase II stage. The null hypothesis is that combination of Daratumumab and DLI has a response rate of < 10% in patients with relapsed AML following allo-HSCT. The alternative hypothesis is that Daratumumab has a response rate of at least 30% in patients with relapsed AML following allo-HSCT. With a type 1 error (alpha): 0.05, and a type 2 error (beta = 1 – power): 0.20, the sample size would be 25 patients for Phase II. If the number of patients achieving ORR is 6 or more, then we reject the null hypothesis. We would include 3-6 patients from

Date of protocol: 10/14/2020

IRB Approval Date: 11/24/2020

Version of protocol: 7

IND number: 139015

Institutional protocol number: OSU 17102

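### Section 16.2 takes consent withdrawals, and week-8 assessments missed for reasons other than early progression, death or toxicity, out of the primary ORR denominator, so ORR can be overstated

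*Combined protocol and SAP*

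**What the plan says.** Section 16.2 (efficacy sets) defines an evaluable patient as an eligible one who "receives at least one dose of Daratumumab, does not withdraw consent, and is evaluated for response week 8". It then keeps, as non-responders, patients with no week-8 assessment because of early progression, death or toxicity. For the rest it states: "Patients who fail to have a week-8 assessment for other reasons (e.g., refusal due to travel constraints) will be considered unevaluable", and leaves them out of the ORR denominator.

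The synopsis definition of efficacy evaluability has the same three conditions but lacks the clause that keeps progression, death and toxicity as non-response.

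Section 12.3 lists reasons for stopping study drug. They include "Unsatisfactory therapeutic response", withdrawal by the subject, protocol violation, loss to follow-up and other. Nothing links these reasons to the categories in Section 16.2.

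The only other ORR planned for the whole cohort is in patients who received at least three daratumumab doses and DLI. Section 16 assumes that 10% will be unevaluable for efficacy.

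**The concern.** The two routes out of the denominator do not depend on whether treatment worked. A patient who withdraws consent because the disease is getting worse is removed. So is one with persistent disease who declines the week-8 marrow without a recorded progression. If such patients respond less often than those who stay, the primary estimate is too high.

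The wording also leaves cases open. The consent clause has no limit on reason or timing. A withdrawal caused by toxicity is therefore excluded by one clause and a non-responder under the next, and a withdrawal after a documented week-8 result is excluded on a literal reading. In an open-label single-arm trial these cases would be settled one by one, by people who know the outcome. The second whole-cohort ORR requires more treatment, so it is more selective and cannot show the effect.

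**Working it through.** **Inputs.** From Section 16: null response rate 10%, alternative 30%, "With a type 1 error (alpha): 0.05", power 0.80, "the sample size would be 25 patients for Phase II", reject the null at 6 or more responders, 10% unevaluable. From Section 16.2: the denominator rule.

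**1. The plan's own design.** Exact binomial:
- P(X ≥ 6 | n = 25, p = 0.10) = 0.0334
- P(X ≥ 6 | n = 25, p = 0.30) = 0.8065

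The smallest single-stage design with one-sided alpha of at most 0.05 and power of at least 0.80 is n = 25 with cut-off 6. At 0.025 per tail it would be n = 29 with cut-off 7. The stated design therefore reproduces as a one-sided test.

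**2. How the rule treats each case.**

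| Situation | Under Section 16.2 |
|---|---|
| Stops treatment, week-8 assessment done, consent kept | In the denominator |
| No week-8 assessment: early progression, death or toxicity | In, as non-responder |
| No week-8 assessment: any other reason | Out |
| Consent withdrawn, any reason or time | Out |
| Consent withdrawn because of toxicity, no week-8 assessment | Out by one clause, non-responder by the next |
| Stops for unsatisfactory response, no recorded progression, no week-8 assessment | Not settled |

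The last row stays open because early progression has no criteria. Sections 7.1 and 16.3 mention only rapidly progressive disease, and the response list on the on-treatment form has resistant disease, stable disease and relapse but no progression entry.

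**3. Effect on the estimate.** Let N be the number treated, R the responders, e the number excluded and r the responders among those excluded. Reported ORR = (R − r)/(N − e). It exceeds R/N only when r/e is below R/N.

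The planned 10% of 25 is 2.5, so take e = 2 or 3, with r = 0 as the upward case (Clopper-Pearson intervals):

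| Responders | All 25 treated | 2 excluded | 3 excluded |
|---|---|---|---|
| 5 | 20.0% (6.8 to 40.7) | 21.7% (7.5 to 43.7) | 22.7% (7.8 to 45.4) |
| 6 | 24.0% (9.4 to 45.1) | 26.1% (10.2 to 48.4) | 27.3% (10.7 to 50.2) |

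The shift is about 2 to 3 percentage points. With 6 responders, the lower limit moves from below to above 10% through exclusions alone.

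If one excluded patient is a responder, the shift reverses: 6/25 = 24.0% becomes 5/24 = 20.8%, 5/23 = 21.7% or 5/22 = 22.7% with 1, 2 or 3 excluded.

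**4. Effect on the decision, 25 treated.** The rule counts responders. Dropping non-responders leaves the count as it was, so type I error stays at 0.0334. Recalculating the cut-off for the smaller set changes nothing either: it remains 6 for n = 21 to 25.

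If exclusions are unrelated to response, ORR is unbiased, but power at 30% falls to 0.731 (n = 23) or 0.687 (n = 22).

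**5. Effect on the decision if places were refilled.** Assume enrolment continues to 25 evaluable, all dropped patients are non-responders, and the true rate among all treated is 10%. The rate among evaluable patients is 0.10/(1 − d), where d is the fraction dropped. At d = 0.10 this is 0.1111, and P(X ≥ 6 | 25, 0.1111) = 0.052. At d = 0.04 and 0.08 (assumed values, 1 and 2 in 25) the error is 0.040 and 0.048.

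All these figures take 25 as the total. Section 16 also carries 3 to 6 phase I patients into the analysis, which could raise it (25 × 0.9 = 22.5, plus 3 to 6, is 25.5 to 28.5 evaluable). That is a separate sample-size question.

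**The case against.** The strongest reply is that Section 16.2 already keeps the main failures. Early progression, death and toxicity all count as non-response, and patients taken off trial for rapid progression would normally fall under the first. This stands, and it limits the problem to the remaining exclusions.

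Four stronger readings are tempting, and the documents do not support them.

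- **Stopping treatment removes a patient.** It does not. The trigger is a missing week-8 assessment or withdrawn consent.
- **Patients stopped for unsatisfactory response are excluded.** Section 12.3 gives reasons for stopping drug, not for missing an assessment. Its list has no progression entry, so this item may well cover progression. The mapping is unsettled, which is not the same as exclusion. Nor do the refusals for lesser toxicities in Section 16.2's tolerability summary show exclusion: a week 8 missed because of toxicity is a non-response.
- **ORR is certain to be overstated.** No figure in the documents gives the response rate among withdrawers. The synopsis allows a second transplant after an early response, so a responder could also miss week 8, and one such patient is enough to reverse the shift.
- **The test's type I error is inflated.** Sections 7.2 and 16 plan to enrol 25 in phase II. Replacement is described only for DLT evaluability in phase I. Step 5 is therefore conditional, and drop-out above 10% has no basis in the plan.

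It is also true that the interval shift at 6 responders changes no decision, because 6 of 25 already meets the rejection rule. What remains is that dosed patients leave the primary denominator for reasons that may be linked to failure, and no planned analysis would show it.

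**Conclusion.** The point holds as a weakness in the definition of the primary endpoint. Consent withdrawals and other-reason missing week-8 assessments leave the denominator, the classification of some cases is contradictory or open, and no all-treated ORR is planned. ORR can be overstated, by about 2 to 3 percentage points at the plan's 10% unevaluable, if those excluded are all non-responders.

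The go/no-go decision is not affected when 25 are treated. The 0.052 needs both refilling and all-non-responder exclusions, neither of which the plan states. The change is worth making because the rule decides who counts in the single primary endpoint and is easy to correct.

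**What to change.** In Section 16.2 and the synopsis:

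- Define the primary ORR denominator as all eligible patients who receive at least one dose of daratumumab.
- Count any patient with no documented response by week 8 as a non-responder, whatever the reason.
- Keep responses documented before consent was withdrawn.
- Report ORR in the present evaluable set as a sensitivity analysis, and for that set state how each Section 12.3 reason, and a toxicity-driven consent withdrawal, is classified.

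The cost is wording only. With 25 treated, the cut-off of 6, the type I error of 0.033 and the power of 0.81 are kept, provided that 10% and 30% are read as rates among all treated patients. The downside is a slightly lower reported ORR, because a patient who misses week 8 for a neutral reason such as travel counts as a failure.

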Date of protocol: 10/14/2020

IRB Approval Date: 11/24/2020

Version of protocol: 7

IND number: 139015

Institutional protocol number: OSU 17102

DLT definition	

• Acute GVHD <math>\geq</math> Grade 3

• Any non-hematologic toxicity <math>\geq</math> Grade 3 related to Daratumumab

• Hematologic toxicity: grade 4 toxicity not related to the underlying disease and not responding to growth factor or transfusion within 7 days

• Grade 3 or higher non-neurologic immune-related adverse events (e.g. diarrhea, pruritus, rash) that responds to corticosteroids and improve to grade 1 or less within 4 weeks will NOT count as DLTs. Optional biopsy of affected organs will be encouraged to help determine whether the immune-related condition is due to GVHD

Enrollment schedule	
Dose level 1: Weekly Dara for eight doses; if no infusional toxicity observed or GVHD observed, proceed to next dose level. 3 patients at a time can be enrolled in one dose level.
 
If no GVHD is observed after at least 2 weeks after DLI, enrollment will proceed to next dose level.

Definitions for safety-evaluability	Received at least one dose of Daratumumab
Definition for DLT evaluability	
All patients are evaluable for DLT except patients who are unable to receive 3 doses of daratumumab in dose level 1, or 3 doses of daratumumab and DLT for dose levels 2 and 3 due to progression of AML.
 
DLT observation period will be from the first dose of daratumumab till 7 days post 3rd dose of daratumumab (for dose level 1) and from the first dose of daratumumab till at least 4 weeks post DLI (for dose level 2 and 3)

Definitions for efficacy evaluability:	All eligible patients who receive at least one dose of Daratumumab, do not withdraw consent, and are evaluated for response at week 8.
Dose-limiting toxicity:	Grade 3 or 4 GVHD
Special situations	

1. If patients attain response before DLI, there will be three options at the discretion of treating physician :

a. Proceed with DLI

Date of protocol: 10/14/2020

IRB Approval Date: 11/24/2020

Version of protocol: 7

IND number: 139015

Institutional protocol number: OSU 17102

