## 9.6 DEFINITIONS OF DOSE LIMITING TOXICITY

Dose limiting toxicity would be development of Grade 3-4 GVHD. GVHD will be graded according to the Glucksberg criteria.

Dose-limiting toxicity is defined as:

- Grade 3-4 Acute GVHD
- Any Grade 3-4 non-hematologic toxicity related to Daratumumab
- Hematologic toxicity: grade 4 toxicity not related to the underlying disease and not responding to growth factor or transfusion within 7 days

Date of protocol: 10/14/2020

IRB Approval Date: 11/24/2020

Version of protocol: 7

IND number: 139015

Institutional protocol number: OSU 17102

Grade 3 or higher non-neurologic immune-related adverse events (e.g. diarrhea, pruritus, rash) that respond to corticosteroids and improve to grade 1 or less within 4 weeks will NOT count as DLTs. Optional biopsy of affected organs will be encouraged to help determine whether the immune-related condition is due to GVHD. Once a patient develops Grade 3-4 GVHD, further enrollment will be on hold until safety and monitoring committee assesses toxicity.

For patients developing Grade 2 GVHD, further doses of Daratumumab will be held until GVHD is controlled. Patients have to meet above-listed criteria before they can resume Daratumumab.

In the phase II expansion part of the study, if >2 patients develop  $\geq$  Grade 3 GVHD, we will stop enrollment and reassess safety.

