## 17 QUALITY CONTROL AND QUALITY ASSURANCE

### Protocol Deviations

The investigator should not deviate from the protocol, except where necessary to eliminate an immediate hazard to study subjects. Should other unexpected circumstances arise that will require deviation from protocol-specified procedures, the investigator should consult with the sponsor or designee (and IRB or IEC, as required) to determine the appropriate course of action. There will be no exemptions (a

Date of protocol: 10/14/2020

IRB Approval Date: 11/24/2020

Version of protocol: 7

IND number: 139015

Institutional protocol number: OSU 17102

prospectively approved deviation) from the inclusion or exclusion criteria. The site should document all protocol deviations in the subject's source documents. In the event of a significant deviation, the site should notify the IRB. Significant deviations include, but are not limited to, those that involve fraud or misconduct, increase the health risk to the subject, or confound interpretation of primary study assessment. A Protocol Deviation Form should be completed by the sponsor or designee for any significant deviation from the protocol.

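### The formal safety dataset in section 16.2 is limited to eligible treated patients, while two other statements cover every treated patient; the three should be aligned on all treated.

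*Combined protocol and SAP*

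**What the plan says.** Three statements in the combined protocol and SAP describe who counts for safety.

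- Section 16.2, under the label for safety sets: "The safety analysis dataset will include all eligible patients who receive one dose of daratumumab".
- Section 16.2, closing the next paragraph, on adverse events and tolerability: "All patients who have received at least one dose of daratumumab will be evaluable for toxicity and tolerability".
- Section 2 (synopsis), row on safety-evaluability: "Received at least one dose of Daratumumab".

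The first requires eligibility; the other two do not. The first also speaks of one dose where the others say at least one. No sentence ranks the three or says how to treat a patient who is found ineligible after dosing.

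**The concern.** A safety population normally contains everyone exposed to the study drug, because harm does not depend on whether an entry criterion was met. The narrower statement here is the one that formally defines the analysis dataset, so it is the one a programmer would most likely implement. The efficacy set, defined just above it, uses *eligible* as a genuine restriction, and the same word one definition later would naturally be read the same way.

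What is at stake is the completeness of the safety summary tables. An exposed patient's adverse events could drop out of them through an eligibility finding made after the events are known. In a study of this size, one patient visibly moves a rate.

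**Working it through.** The plan states no figure on this point, so the check is a comparison of text followed by an illustration.

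**Step 1. The three statements side by side**

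| Place | What it defines | Dose condition | Eligibility condition |
|---|---|---|---|
| 16.2, safety sets | analysis dataset | one dose | yes |
| 16.2, next paragraph | evaluability for toxicity | at least one dose | none |
| Synopsis | safety-evaluability | at least one dose | none |

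A patient who is dosed and later found ineligible is out under the first row and in under the second and third. Every other treated patient is treated alike under all three, if one dose is read as at least one.

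**Step 2. Where the word reaches**

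- Dose escalation. The synopsis says "All patients are evaluable for DLT except patients who are unable to receive 3 doses of daratumumab in dose level 1", then gives the matching condition for levels 2 and 3. The replacement rule in section 16 turns on doses received. Neither mentions eligibility.
- Phase II GVHD trigger. Section 9.6 begins "In the phase II expansion part of the study, if >2 patients develop" and goes on to GVHD of grade 3 or worse. It counts patients, without an eligibility condition.
- Data capture. Section 13.6 requires every adverse event after exposure to be recorded in the CRF.
- Primary phase II test. It uses the efficacy set. The plan says "the sample size would be 25 patients for Phase II", with rejection at 6 or more responders. The exact binomial check at response rates of 10% and 30% gives one-sided alpha 0.0334 and power 0.8065, consistent with the stated 0.05 and 0.80. The safety set plays no part in this.

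Only the safety summary tables can change.

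**Step 3. Illustration**

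Inputs: n = 25 treated, taken from the phase II size. Assumed, because the documents give neither: x = 3 patients with some severe toxicity, and k = 0 to 3 treated patients later found ineligible, of whom j had the event.

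All-treated rate = x/n. Eligible-only rate = (x − j)/(n − k). Exact (Clopper-Pearson) 95% intervals are given for the all-treated rate and for the column where every removed patient had the event.

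| k removed | All had the event (j = k) | None had the event (j = 0) |
|---|---|---|
| 0 | 3/25 = 12.0% (2.5 to 31.2) | same |
| 1 | 2/24 = 8.3% (1.0 to 27.0) | 3/24 = 12.5% |
| 2 | 1/23 = 4.3% (0.1 to 21.9) | 3/23 = 13.0% |
| 3 | 0/22 = 0% (0 to 15.4) | 3/22 = 13.6% |

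The rate falls when the removed patients have the event more often than the group as a whole (j/k > x/n), and rises when they have it less often. The left-hand column is the one-sided worst case.

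**The case against.** The strongest reply is that the intended population is already clear. Two of three statements cover all treated patients, one of them in the paragraph directly after the restrictive sentence, and the word *eligible* looks carried over from the efficacy definition above. All events are recorded, so no data are lost. Section 17 allows no prospective exemptions from the entry criteria, so there may be no ineligible treated patients at all.

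Most of this stands, and it is why the point is minor. It does not remove the conflict. The later sentence does not say that it overrides the dataset definition, and being evaluable is not the same label as being in the analysis dataset. A ban on waivers does not cover ineligibility discovered after dosing.

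A reader might also infer more than the documents support:

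- That never-transplanted patients at dose level 1 would leave the safety set because they cannot meet the donor-chimerism criterion. Both the synopsis and section 8.1 expressly declare these patients eligible at that level, and a criterion on donor cells has no natural application to someone without a donor. Its wording is a separate drafting matter.
- That the number removed depends on which eligibility list is used. For that group it does not: the level 1 inclusion and the chimerism exclusion appear in both lists. The lists differ on some other items, but nothing in the documents turns those differences into a count of treated, ineligible patients.
- That dose finding is distorted. Step 2 rules this out.

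**Conclusion.** The inconsistency is real and sits in the current text. Read literally, the formal definition keeps treated patients later found ineligible out of the safety summary tables, against the plan's two other statements. The consequence is confined to those tables and arises only if such a patient exists; the documents give no expected number, and with none the effect is nil. The illustrated shift from 12.0% to 8.3% or to 12.5% for one removed patient rests on assumed counts and shows scale only. It would be tempting to say that the definition understates toxicity. That does not follow in general, since the direction depends on whether the removed patients had the event. What can be said is that exposed patients' safety information could be left out, and that the plan does not settle whether it will be.

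**What to change.** In the section 16.2 sentence that defines the safety set, delete *eligible*, change one dose to at least one dose, and add that patients are included regardless of eligibility. All three statements then agree, and the handling of a patient found ineligible after dosing is settled in advance. The cost is an edit to one sentence. It needs no new data, because section 13.6 already captures the events, and it leaves the sample size, alpha, power, DLT rules and GVHD trigger as they are.
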